Appendix Table 3: Schedule of Assessments for Arm C (Pamiparib and Temozolomide)

Study Phase	Screening ^a	Treatment ^b								End of Treatment ^c	Safety Follow-up ^d	Long-Term Follow-up ^d
		Cycle 1				Cycle 2		Cycle ≥3				
		D1	D8	D15	D22	D1	D15	D1	D15			
Allowed time window			± 2	± 2	± 2	+ 2	± 2	± 3	± 3			
Study Day	-28 to -1	1	8	15	22	29	43	57	71	Varies	Varies ^d	Varies ^d
Informed consent	X											
Patient enrollment	X ^a											
Demographics and medical history	X											
Complete physical examination ^e	X					X		X		X		
Limited physical examination ^e		X	X	X	X		X		X			
Vital signs and weight ^f	X	X	X	X	X	X	X	X	X	X		
Height	X											
ECOG performance status	X	X				X		X		X		
12-lead ECG	X (-14 to -1)	X				X		X		X		
Hematology ^g	X (-14 to -1)	X	X	X	X	X	X	X	X	X	X	
Chemistry ^h	X (-14 to -1)	X	X	X	X	X	X	X		X	X	
Coagulation (INR and aPTT)	X (-14 to -1)					X				X		
Hepatitis B serology ⁱ	X (-14 to -1)											
Urinalysis ^j	X (-14 to -1)					X		X		X		
Pregnancy testing ^k	X (-7 to -1)					X		X		X	X	
MRI scan ^l	X (-14 to -1)							X (q8w ±7d)		X		X (q8w ±7d)
Patient registration	X ^a											
Pamiparib ^m		X	X	X	X	X	X	X	X			
Temozolomide (TMZ) ⁿ		X	X	X		X	X	X	X			
Adverse events ^o	X ^o	X	X	X	X	X	X	X	X	X	X ^o	X ^o

Appendix Table 3: Schedule of Assessments for Arm C (Pamiparib and Temozolomide) (Continued)

Study Phase	Screening ^a	Treatment ^b								End of Treatment ^c	Safety Follow-up ^d	Long-Term Follow-up ^d
		Cycle 1				Cycle 2		Cycle ≥3				
		D1	D8	D15	D22	D1	D15	D1	D15			
Concomitant medication(s) ^p	X	X	X	X	X	X	X	X	X	X	X ^p	X (~q12w) ^p
Pharmacokinetics ^q		X		X								
Blood for biomarkers ^r	X	X		X				X		X		
Tumor tissue ^s	X											
Survival follow-up												X (~q12w)

7/-14 to -1, Day -7/-14 to Day -1 of screening; aPTT, activated partial thromboplastin time; CSF, cerebrospinal fluid; D, day; ECG, electrocardiogram; ECOG, Eastern Cooperative Oncology Group; INR, International Normalized Ratio; MRI, magnetic resonance imaging; q8w ±7d, every 8 weeks ± 7 days; ~q12w, approximately every 12 weeks

^a Screening must occur within 28 days of Day 1. Assessments obtained within 14 days of Day 1 (pregnancy and laboratory assessments: within 7 days) do not have to be repeated on Day 1. Some assessments have a narrower screening window as shown in the table. It is highly recommended that general screening assessments such as physical examination and laboratory assessments should be conducted first to rule out ineligibility based on those grounds before more involved and/or invasive procedures are carried out.

^b Cycle 1 encompasses the dose-limiting toxicity (DLT) assessment window, and assessments of Day 1 of Cycle 2 at the end of the DLT assessment window are required for a patient to be DLT-evaluable. Assessments shown for Cycle 3 apply to all subsequent cycles except for MRI that occurs every second cycle (every 8 weeks).

^c The end-of-treatment (EOT) visit will occur within 7 days after a patient discontinued study treatment for any of the reasons outlined in [Section 6.5.1](#). A visit should be scheduled as soon as possible, but the EOT visit may occur later after discussion with the medical monitor for specific circumstances, such as prolonged hospitalization. The visit at which MRI showed progressive disease (PD) may be used as the EOT visit provided that all required assessments were performed. MRI does not have to be repeated if it was performed within 14 days of the EOT visit or at a prior response evaluation that documented PD. ECG does not have to be repeated if it was performed within 14 days of the EOT visit.

^d **Safety Follow-up:** all patients who discontinue study treatment will have a safety follow-up visit approximately 30 (±7) days after the last day of study treatment to collect AEs and SAEs that may have occurred after the patient discontinued from the study treatment.

Long-Term Follow-up: Patients who were not discontinued from study treatment due to PD and meet criteria otherwise (eg, discontinued for AE and no new anticancer therapy) will be followed every 8 weeks (±7 days) until disease progression, administrative issues, start of other anticancer therapy or any other reason listed in [Section 6.7](#), whichever occurs first.

Patients will be followed for survival and further anticancer therapy information post progression via phone contact (with the patient’s guardian, if applicable) approximately every 12 weeks.

^e A complete physical examination should include an evaluation of head, eyes, ears, nose and throat, neck, heart, chest (including lungs), abdomen, extremities, skin,

lymph nodes, cardiovascular status and neurological status. A limited physical examination should include neurological status, and additionally be directed at the evaluation of symptoms or specific safety issues. Changes from baseline abnormalities should be recorded at each subsequent physical examination. New or worsened abnormalities should be recorded as AEs if appropriate.

- ^f Vital signs (systolic and diastolic blood pressure; pulse rate; and oral, temporal or tympanic temperature) will be taken before study treatment and approximately 15 minutes prior to each collection of PK blood samples, if applicable, during the treatment period.
- ^g Hematology includes hemoglobin, platelet count, white blood cell (WBC) count, neutrophil count, and lymphocyte count. For cycle 2 and beyond hematology is only required on Days 1 and 15 however should be measured more frequently based on the patient's blood counts and need for additional monitoring. Per the [Temodar prescribing information](#), hematology also needs to be completed on Day 22 which is 21 days after the first dose.
- ^h Chemistry includes albumin, alkaline phosphatase, aspartate aminotransferase (AST), alanine aminotransferase (ALT), blood urea nitrogen (BUN), chloride, creatinine, glucose, lactic acid dehydrogenase (LDH), phosphate, potassium, sodium, total bilirubin, and total protein.
- ⁱ Testing will be performed by the local laboratory at Screening and will include HBV serology (HBsAg, HBsAb, and HBcAb) and viral load assessment (HBV DNA).
- ^j Urinalysis will be assessed using urine dipstick. Urine microscopy will be performed if any assessment on the urine dipstick is abnormal. Urinalysis includes glucose, protein, ketones, bilirubin, blood, red blood cells, and white blood cells.
- ^k For women of childbearing potential, a serum pregnancy test must be performed during screening ≤ 7 days prior to Day 1. For subsequent pregnancy testing while on study treatment and at end of treatment, urine pregnancy tests are acceptable. If a urine pregnancy test is positive, a confirmatory serum pregnancy test is required.
- ^l Tumors will be assessed at screening by MRI per RANO criteria within 14 days prior to Day 1, then every 8 weeks (± 7 days) and as part of the EOT visit. Patients without PD at the EOT visit must then be followed with MRIs every 8 weeks (± 7 days) during the Follow-up Phase.
- ^m All patients will receive daily pamiparib as outlined in [Section 4](#). Patients will continue receiving pamiparib in combination with TMZ in Arm C until PD, unacceptable toxicity or death, withdrawal of consent, loss to follow-up, or study termination by sponsor. Patients will be required to fast for at least 1 hour before and 2 hours after each pamiparib administration. Water is allowed during the fasting period. A dose of pamiparib should be skipped if it is not taken within 2 hours of the scheduled time. An extra dose of pamiparib should not be taken to make up for a missed dose. If vomiting occurs during the course of treatment, no re-dosing of the patient is allowed before the next scheduled dose. On days with PK assessments, pamiparib should be administered in the clinic.
- ⁿ All patients will receive temozolomide (TMZ) at a dose level as outlined in [Section 4](#). TMZ will be given for Days 1 to 21 of each 28-day cycle. Instructions for TMZ administration are the same as for pamiparib. Antiemetic prophylaxis may be provided as described in [Section 7.1.2.3](#). On days with PK assessments, TMZ should be administered in the clinic.
- ^o Adverse events and laboratory safety measurements will be recorded at each study visit, graded per NCI-CTCAE Version 4.03 and assessed as outlined in [Section 10](#). After informed consent has been signed but prior to study treatment, only SAEs should be reported. After initiation of study treatment, all AEs and SAEs, regardless of relationship to study treatment, will be reported until 30 days after last study treatment or initiation of new anticancer therapy, whichever occurs first. After this period, the investigator should report any SAEs that are believed to be related to prior study treatment.
- ^p Concomitant medications will be recorded at each study visit. All concomitant medications taken by or administered to the patient within 28 days before Day 1 and 30 days after the last day of study treatment should be recorded. The eCRF entry must include the dose, regimen, route, indication, and start and stop dates of use of the prior and concomitant medications. Concomitant medications include subsequent anticancer therapy information acquired during the Follow-up Phase.
- ^q Pharmacokinetic samples will be collected from patients in all cohorts at the following time points: predose (within 30 min prior to dose) and 2 hours (± 30 min) post-dose on both Cycle 1 Day 1 and Cycle 1 Day 15. If pamiparib treatment is administered for only 2 weeks (14-day) time period, PK samples will be collected on Day 1 and Day 14 instead. The time of study drug administration on the day prior to Cycle 1 Day 15 (Day 14 if pamiparib is administered for 2 weeks) must be recorded on

the eCRF. Details concerning collection, processing, and handling of the PK plasma samples will be provided in the laboratory manual.

- r Blood samples must be collected at screening or on Day 1 (5 mL) for the assessment of germline mutations. Additionally, 3 blood samples (10 mL each) must be collected for the assessment of circulating tumor cells (CTCs) and plasma markers (eg, circulating nucleic acids [CNAs]) of GBM, TMZ treatment, and PARP inhibition at screening or on Day 1 before study treatment, and 2 blood samples (10 mL each) must be collected for the assessment of plasma markers (eg, CNAs) of GBM on Day 15 and Cycle 3 Day 1 before study treatment and at the EOT visit (unless one had been collected within 14 days). Instructions for the processing, storage, and shipping of samples will be provided in the laboratory manual.

s

Appendix Table 4: Schedule of Assessments for Maintenance Treatment for Arms A and B (Pamiparib In Combination With Temozolomide)

Study Phase	Re-Screening ^a	Treatment					End of treatment (EOT) Visit ^b	Safety Follow-up ^c	Long-term Follow-up ^c
		Cycle 1		Cycle 2		Cycle ≥3			
		Day 1	Day 15	Day 1	Day 15	Day 1			
Allowed time window			± 3	± 3	± 3	± 3			
Re-Treatment Study Day		1	15	28	43	57	Varies	Varies ^c	
Patient enrollment	X								
Complete physical examination ^d	X	X	X	X	X	X			
Vital signs and weight ^e	X	X	X	X	X	X	X		
ECOG performance status	X	X	X	X	X	X	X		
12-lead ECG	X	X					X		
Hematology ^f	X	X	X	X	X	X	X	X	
Chemistry ^g	X	X	X	X	X	X	X	X	
Urinalysis ^h	X	X					X		
Pregnancy testing ⁱ	X			X		X	X	X	
MRI scan ^j	X					X (q8w ±7d)	X	X (q8w ±7d)	
Pamiparib ^k		X	X	X	X	X			
Temozolomide (TMZ) ^l		X	X	X	X	X			
Adverse events ^m	X	X	X	X	X	X	X	X ^m	
Concomitant medication(s) ⁿ	X	X	X	X	X	X	X	X ⁿ	
Survival follow-up								X (~q12w) ⁿ	
Tumor tissue ^o							X ^o		

Appendix Table 4: Schedule of Assessments for Maintenance Treatment for Arms A and B (Pamiparib In Combination With Temozolomide) (Continued)

7/-14 to -1, Day -7/-14 to Day -1 of screening; aPTT, activated partial thromboplastin time; CSF, cerebrospinal fluid; D, day; ECG, electrocardiogram; ECOG, Eastern Cooperative Oncology Group; INR, International Normalized Ratio; MRI, magnetic resonance imaging; q8w ±7d, every 8 weeks ± 7 days; ~q12w, approximately every 12 weeks

- ^a Maintenance treatment should commence following the 4-week rest period post-completion of RT (+7 days) to allow for recovery from RT treatment. A re-screening to confirm continued eligibility must occur within 7 days prior to commencing maintenance treatment. The EOT visit post-completion of the post RT rest period may be considered the re-screening visit provided all assessments were completed. Patients' must continue to meet eligibility criteria prior to commencing maintenance treatment.
- ^b The end-of-treatment (EOT) visit will occur within 7 days after a patient discontinued study treatment for any of the reasons outlined in [Section 6.5.1](#). A visit should be scheduled as soon as possible, but the EOT visit may occur later after discussion with the medical monitor for specific circumstances, such as prolonged hospitalization. The visit at which MRI showed progressive disease (PD) may be used as the EOT visit provided that all required assessments were performed. MRI does not have to be repeated if it was performed within 14 days of the EOT visit or at a prior response evaluation that documented PD. ECG does not have to be repeated if it was performed within 14 days of the EOT visit.
- ^c **Safety Follow-up:** all patients who discontinue study treatment will have a safety follow-up visit approximately 30 (±7) days after the last day of study treatment to collect AEs and SAEs that may have occurred after the patient discontinued from the study treatment.
- Long-Term Follow-up:** Patients who were not discontinued from study treatment due to PD and meet criteria otherwise (eg, discontinued for AE and no new anticancer therapy) will be followed every 8 weeks (±7 days) until disease progression, administrative issues, start of other anticancer therapy or any other reason listed in [Section 6.7](#), whichever occurs first.
- Patients will be followed for survival and further anticancer therapy information post progression via phone contact (with the patient's guardian, if applicable) approximately every 12 weeks.
- ^d A limited physical examination should include neurological status, and additionally be directed at the evaluation of symptoms or specific safety issues. Changes from the EOT visit of the escalation portion should be recorded. New or worsened abnormalities should be recorded as AEs if appropriate.
- ^e Vital signs (systolic and diastolic blood pressure; pulse rate; and oral, temporal, or tympanic temperature) will be taken before study treatment during the treatment period.
- ^f Hematology includes hemoglobin, platelet count, white blood cell (WBC) count, neutrophil count, and lymphocyte count. For maintenance cycle 2 and beyond hematology is only required on Days 1 and 15 however should be measured more frequently based on the patient's blood counts and need for additional monitoring. Per the [Temodar prescribing information](#), hematology also needs to be completed on Day 22 which is 21 days after the first dose.
- ^g Chemistry includes albumin, alkaline phosphatase, aspartate aminotransferase (AST), alanine aminotransferase (ALT), blood urea nitrogen (BUN), chloride, creatinine, glucose, lactic acid dehydrogenase (LDH), phosphate, potassium, sodium, total bilirubin, and total protein.
- ^h Urinalysis will be assessed using urine dipstick. Urine microscopy will be performed if any assessment on the urine dipstick is abnormal. Urinalysis includes glucose, protein, ketones, bilirubin, blood, red blood cells, and white blood cells.
- ⁱ For women of childbearing potential, a serum pregnancy test must be performed during re-screening ≤ 7 days prior to Day 1. For subsequent pregnancy testing while

- on study treatment and at end of treatment, urine pregnancy tests are acceptable. If a urine pregnancy test is positive, a confirmatory serum pregnancy test is required.
- j The scheduling of MRIs during the maintenance phase should continue on an 8 week schedule; ie, the first MRI during maintenance should be completed 8 weeks after the EOT MRI conducted after the rest period following completion of RT. Tumors will be assessed by MRI per RANO criteria every 8 weeks (\pm 7 days). Patients without PD at the EOT visit must be followed with MRIs every 8 weeks (\pm 7 days) during the Follow-up Phase. The EOT MRI should only be collected if an MRI has not been performed within 8 weeks or if PD is suspected.
 - k All patients will receive daily pamiparib as outlined in [Section 4](#). Patients will continue receiving pamiparib in combination with TMZ until PD, unacceptable toxicity or death, withdrawal of consent, loss to follow-up, or study termination by sponsor. Patients will be required to fast for at least 1 hour before and 2 hours after each pamiparib administration. Water is allowed during the fasting period. A dose of pamiparib should be skipped if it is not taken within 2 hours of the scheduled time. An extra dose of pamiparib should not be taken to make up for a missed dose. If vomiting occurs during the course of treatment, no re-dosing of the patient is allowed before the next scheduled dose.
 - ^l All patients will receive temozolomide (TMZ) at a dose level lower than or equal to a dose that has been determined to be safe and tolerable in Arm C of study.
 - ^m Adverse events and laboratory safety measurements will be recorded at each study visit, graded per NCI-CTCAE Version 4.03 and assessed as outlined in [Section 10](#). After initiation of study treatment, all AEs and SAEs, regardless of relationship to study treatment, will be reported until 30 days after last study treatment or initiation of new anticancer therapy, whichever occurs first. After this period, the investigator should report any SAEs that are believed to be related to prior study treatment.
 - ⁿ Concomitant medications will be recorded at each study visit. All concomitant medications taken by or administered to the patient until 30 days after the last day of study treatment should be recorded. The eCRF entry must include the dose, regimen, route, indication, and start and stop dates of use of the prior and concomitant medications.
 - ^o If the patient undergoes repeat resection on completion of the maintenance phase, tumor tissue may be collected for the assessment of markers related to GBM, TMZ treatment, and PARP inhibitors.

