6.4. Unscheduled Visit

Unscheduled visits may occur any time as necessary as per investigator decision or patient's request for reasons such as additional assessment or follow-up of AEs. If PD is suspected an MRI should be performed

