8. STUDY ASSESSMENTS

8.1. Study Flow and Visit Schedule

The study-specific assessments and procedures with allowed time windows for Arm A, Arm B, and Arm C, and maintenance treatment for Arms A and B are outlined in [Appendix Table 1](#), [Appendix Table 2](#), [Appendix Table 3](#), and [Appendix Table 4](#), respectively. Assessment of safety of the combination therapies will be based on AE monitoring and reporting (including attribution of AEs and serious adverse events [SAEs]), clinical laboratory testing, vital signs, ECGs, physical examinations, and PK assessments as outlined in [Sections 8.2](#), [8.4](#), and [8.5](#), as well as [Appendix 1](#). Assessments of efficacy will occur as outlined in [Section 8.3](#) and [Appendix 1](#).

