8.4.4. Laboratory Studies

Samples for hematology, chemistry, and coagulation profiles will be drawn and analyzed locally. All other required blood samples will be sent to a central laboratory for analysis throughout the study.

A detailed description of the procedures for sample collection, handling, storage, and shipment of the laboratory samples and all material such as test tubes and labels is provided in the laboratory manual.

Laboratory studies will be performed at the time points specified in [Appendix 1](#) (including allowed windows of assessment) and may also be performed as medically necessary. Laboratory assessments should be done before study treatment. Screening blood and urine tests must be performed within

14 days of Day 1. If they were performed within 7 days of Day 1, they do not need to be repeated on Day 1.

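### Maintenance schedule for Arms A and B (Protocol Appendix Table 4): from Cycle 3 the grid has hematology on Day 1 only, while footnote f on the same row requires Days 1 and 15.

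*Protocol*

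**What the plan says.** Protocol Appendix Table 4 is headed as the "Schedule of Assessments for Maintenance Treatment for Arms A and B". Its treatment columns are Cycle 1 Days 1 and 15, Cycle 2 Days 1 and 15, and Cycle ≥3 Day 1. The hematology row is marked at each of these, and also at re-screening, end of treatment and safety follow-up. There is no Day 15 column from Cycle 3.

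Footnote f, attached to that row, gives a different minimum: "For maintenance cycle 2 and beyond hematology is only required on Days 1 and 15". It adds that testing should be more frequent according to the patient's "blood counts and need for additional monitoring", and it separately asks for a Day 22 count.

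The body of the protocol does not settle the matter:

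- Section 8.1 says only that the assessments "and maintenance treatment for Arms A and B are outlined in" the appendix tables.
- Section 8.4.4 refers to Appendix 1 for timing and says that laboratory studies "may also be performed as medically necessary".
- Section 6.4 says: "Unscheduled visits may occur any time as necessary as per investigator decision".

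In Arm C, footnote g of Appendix Table 3 states the same rule: "For cycle 2 and beyond hematology is only required on Days 1 and 15". There the grid has both Day 1 and Day 15 under Cycle ≥3, and hematology is marked at both.

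**The concern.** Two parts of one table give different minimum testing frequencies for the same row, and no text ranks grid over footnote. Site staff commonly book visits from the grid, and from Cycle 3 it contains no visit at which the footnote's Day 15 count could be taken.

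The stake is safety monitoring. Protocol Section 1.2.4 names bone marrow toxicity as the dose-limiting factor of chemotherapy in this disease. Footnote k of Appendix Table 4 lets maintenance run until progression, unacceptable toxicity or another stopping reason, so Cycle 3 onward may be most of a patient's time on treatment. The dose-modification table in Section 7.1.5.3 calls for both drugs to be held at Grade 3 anemia, neutropenia or thrombocytopenia, and at repeat Grade 2 anemia. Those rules act only once a count has been taken. The weekly counts in Section 10.1.4 concern toxicity already found, so the issue is first detection.

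**Working it through.** **Is the missing column real?** Three features of the Appendix Table 4 grid agree: the header has five treatment-day labels, the study-day row has five values (1, 15, 28, 43, 57), and the fully marked rows have one mark under Cycle ≥3. Arm C's grid has study days 57 and 71 for Cycle ≥3; the maintenance grid stops at 57. This is how the table was written and not a conversion fault.

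**Inputs**

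- Maintenance cycle length: 28 days (SAP Section 6.2.4).
- Visit window: ±3 days on the later maintenance visits (Appendix Table 4). I assume the same window for a Cycle ≥3 Day 15 visit.
- Grid: 2 counts in Cycle 1, 2 in Cycle 2, 1 in each later cycle.
- Footnote f: Days 1 and 15 from Cycle 2 onward. Cycle 1 also has Days 1 and 15 in the grid.
- Left out of both tallies: the Day 22 count, re-screening, end of treatment and safety follow-up.

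**Interval between routine counts from Cycle 3**

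- Grid, Day 1 to next Day 1: 28 days; with windows, 28 − 3 − 3 = 22 to 28 + 3 + 3 = 34 days.
- Footnote, Day 1 to Day 15: 14 days; with windows, 14 − 6 = 8 to 14 + 6 = 20 days.

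**Routine counts over N completed cycles (N ≥ 3)**

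- Grid: 2 + 2 + (N − 2) = N + 2.
- Footnote: 2N.
- Difference: 2N − (N + 2) = N − 2.

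The documents give no maintenance duration, so these values of N are assumptions:

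| N (assumed) | Grid, N + 2 | Footnote, 2N | Fewer by |
|---|---|---|---|
| 3 | 5 | 6 | 1 |
| 6 | 8 | 12 | 4 |
| 12 | 14 | 24 | 10 |

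**Ceiling on patients.** SAP Section 5 gives 40 patients in the Arm A expansion and 46 in Phase 1b across all arms. The sum is 40 + 46 = 86, from which the Arm C escalation patients, whose number is not given, must be taken off. SAP Section 8 says the Arm B expansion, the one cohort with mandatory maintenance, was not enrolled. In Arm A, maintenance is at the investigator's discretion (Protocol Section 4.1.2). The number exposed is therefore below 86 and further limited to patients who reach maintenance Cycle 3 at a site working from the grid.

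**Which rule was meant?** Arm C gives the same drugs under the same footnote sentence, and its Cycle ≥3 Day 15 visit keeps hematology while leaving chemistry blank. The authors kept the mid-cycle blood count there while leaving out another laboratory test. Nothing in the documents argues for halving the counts in maintenance. The footnote is the likely intent.

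**The case against.** The best reply is that the requirement is already stated. Footnotes in Appendix 1 do add to the grids: in Arm A, footnote q moves a pharmacokinetic sample to Day 14, and footnote r asks for biomarker blood on Day 36 with no mark in the row. Read that way, footnote f simply adds Cycle ≥3 Day 15, just as it adds Day 22, and a careful site draws both counts. Much of this stands. The table can be followed correctly, the defect is an incomplete grid, and no document shows any site testing too little. But this reading leads to the same Day 15 count, and it relies on every site finding in a footnote a recurring visit that the grid omits. The allowances for extra or unscheduled tests depend on judgment and schedule nothing.

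Some stronger readings are tempting but not supported:

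- **That both drugs run on unchecked until the next Day 1.** Appendix Table 4 gives a temozolomide dose level for maintenance but no dosing days. In Arm C temozolomide stops at Day 21, and Section 4.2.1 allows that regimen to be applied in Phase 2 Arms A and B. One can say only that pamiparib would continue, and temozolomide on its dosing days.
- **That the Day 22 count is a second contradiction.** The footnote adds that time point and no grid entry opposes it.
- **That no endpoint of any kind is touched.** Laboratory changes are a Phase 1b primary and a Phase 2 secondary endpoint (Protocol Sections 3.1 and 3.2), and SAP Section 6.5.4 summarizes the worst postbaseline grade. Fewer counts could miss a worse grade.

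**Conclusion.** The inconsistency is real, and small. From maintenance Cycle 3 the grid provides half the routine blood counts that its own footnote requires: one per 28 days against one per 14. For a patient completing N cycles that is N − 2 fewer counts, or 1, 4 or 10 for an assumed 3, 6 or 12 cycles.

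The consequence is conditional. It needs a site that schedules from the grid alone and orders no discretionary counts, and a patient who reaches Cycle 3. How many such patients there are is unknown. Where it applies, first detection of a cytopenia calling for a hold could be delayed. A reader might infer that patients were in fact under-monitored; the documents do not show that.

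Efficacy endpoints, power and error rates are unaffected. Laboratory safety summaries could be ascertained unevenly if sites read the table differently, by an amount that cannot be estimated from the documents.

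**What to change.** Add a Day 15 hematology mark under Cycle ≥3 in the Appendix Table 4 grid, in line with footnote f and with Arm C's hematology row. Tell sites with patients still on maintenance that Days 1 and 15 apply. The mark need not copy the whole Arm C Day 15 visit, which also carries a limited examination, vital signs and other items; footnote f asks only for the blood count.

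Leave the Day 22 sentence as it stands. Confining it to Cycle 1 would narrow a safety requirement that the footnote leaves unqualified.

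The cost is a table correction, a short site notice, and one extra local blood draw with a brief visit per cycle from Cycle 3, only at sites now following the grid. SAP Section 5 reports the number enrolled as final and does not say whether anyone remains on maintenance. If no one does, only the table correction is left.
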